## 5.7 Risk/Benefit Assessment

#### 5.7.1 Risks associated with Study device

Complications and reactions are possible with any soft tissue repair, including but not limited to: infection, increased chronic inflammation, allergic reaction, unexplained fever or chills, excessive redness, acute and chronic pain, swelling, tender scars, adhesions, seroma formation, fistula formation, hematoma, recurrence of tissue defect, delayed or failed incorporation of graft, urinary or fecal incontinence,

delayed or failed incorporation of graft, mesh or suture erosion or extrusion, and injury to the bladder, bowel, blood vessels.

#### 5.7.2 Risks Associated with Participation in the study and mitigation

As this retrospective study involves data collection, there are only minimal risks associated with participation. There are no additional device-related risks for this study. There are, however, privacy (loss of confidentiality) risks associated with participation in the study.

Participation in the study does not submit the patient to any additional procedures or exams outside the customary standard of care. Patient confidentiality and privacy is strictly held in trust by the participating investigator, their staff, and the Sponsor. The patient's data will be given a code to assure that the data can only be traced with the use of an identifier. The identifier will be stored securely in the local research institute. Data that is shared with the sponsor will only contain the code. The patient's name and any other identifiable information will be omitted. All national data protection laws will be respected including the US Health Insurance Portability and Accountability Act of 1996 (HIPAA). Data shared with the sponsor will be encoded and maintained in a secure electronic database that is compliant with 21 CFR Part 11 requirements on electronic records and electronic signatures.

#### 5.7.3 Anticipated Clinical and device Benefits

There is no direct benefit. Information learned from this study might help researchers to better understand medical treatments and disease processes or procedures in order to better help others in the future.

The data collected from the study will be used to inform the device manufacturer about the safety and performance of the device when used in accordance with the device labelling.

#### 5.7.4 Rationale of Risks/Benefits Ratio

The participation in the study does not add risks to the patients, thus the benefit is judged to outweigh the overall residual risks.

T-GENVIH-002 study

Confidential

# 6 Study Assessments and Procedures

#### 6.1 Schedule of Data Collection

### 6.1.1 Screening

- The procedures to be completed are:
  - ✓ Retrospective chart review will include the full consecutive series of patients between 22 years and 80 years old who underwent abdominal wall reconstruction for a hernia with Integra Gentrix® Surgical Matrixbetween November 1, 2017, and present (90 days prior).
  - ✓ Creation on the eCRF of a new case book for each eligible subject. Each created case book assigns the eligible subject with a study number.
  - ✓ Completion of Worksheets/ eCRFs: Site will transcribe/transmit the below-mentioned patients' data in study worksheets & eCRFs. The patients' data will originate from existing medical and other patient records.
- The patients' data to be collected are:
  - ✓ Eligibility:
    - o Inclusion Criteria: Ensure the subject meets the inclusion criteria.
    - o Exclusion Criteria: Ensure the subject does not meet any of the exclusion criteria.
  - ✓ Demographics: gender, year of birth, height, weight, race, ethnicity, nicotine and alcohol use history.
  - ✓ Medical history: Obtain subject 's medical history up to 3 years prior to surgery. Medical history is considered relevant when related to any of the study eligibility criteria, or when it may affect any of the clinical investigation endpoints, at the discretion of the investigator. Relevant medical history covers at a minimum Ventral Hernia related medical history treated in this study.

## 6.1.2 Index Surgery

The patients' data to be collected at the index surgery are:

- Ventral Hernia Details: Location and size of the ventral hernia(s), CDC Wound Class (the highest one) and complications associated with Hernia(s) repair.
- Surgery Details: Surgical approach (Robotic, Laparoscopic, Robotic assisted, Laparoscopic assisted, MIS converted to open, Open), Times related to the different steps of the index surgery.
- Type of the Gentrix Surgical Matrix Used.

- Intraoperative Details: Surgical Plane of graft placement, Graft fixation, Component separation,
   Concomitant procedure, Stoma presence, and Fascial closure.
- Adverse Events: Information will be collected on any adverse event that the subject is experiencing during or after the surgical procedure.
- Device Deficiency: Medical records will be reviewed for DDs that were documented during the timeframe of treatment with the subject device.

Note: Completion of Worksheets/ eCRFs: Site will transcribe/transmit the above-mentioned patients' data in study worksheets & eCRFs. The patients' data will originate from existing medical and other patient records.

#### 6.1.3 Discharge

Since the index surgery, the patients' data to be collected at discharge are:

- Post-operative complications requiring procedural intervention
- Post-operative complications (Surgical Site Occurrences)
- Surgical Site Infections (SSIs)
- · Hernia recurrence confirmed by clinical assessment
- Reoperations due to index repair
- Adverse Events: Information will be collected on any adverse event that the subject is experiencing during or after the surgical procedure.
- Concomitant Medications: Immunomodulators as well as opioids.

Note: Completion of Worksheets/ eCRFs: Site will transcribe/transmit the above-mentioned patients' data in study worksheets & eCRFs. The patients' data will originate from existing medical and other patient records.

#### 6.1.4 Follow-Up Visit

The time frame for follow up visits is up to 1 year or shorter, as applicable.

Since previous visit, the patients' data to be collected at the follow-up visit(s) are:

- Post-operative complications requiring procedural intervention
- Post-operative complications (Surgical Site Occurrences)
- Surgical Site Infections (SSIs)
- · Hernia recurrence confirmed by clinical assessment
- Reoperations due to index repair

**Integra LifeSciences** 

INTEGRA

 Adverse Events: Information will be collected on any adverse event that the subject is experiencing during or after the surgical procedure.

• Concomitant Medications: Immunomodulators as well as opioids.

Note: Completion of Worksheets/ eCRFs: Site will transcribe/transmit the above-mentioned patients' data in study worksheets & eCRFs. The patients' data will originate from existing medical and other patient records.

#### 6.1.5 Study exit

The patients' data to be collected at study exit are:

Study Exit Type

Note: Completion of Worksheets/ eCRFs: Site will transcribe/transmit the above-mentioned patients' data in study worksheets & eCRFs. The patients' data will originate from existing medical and other patient records.

#### 6.2 Concomitant Medication Review

Only immunomodulators and opioids are to be reported on the Concomitant Medication (ConMed) CRF.

# 6.3 Monitoring

Clinical site monitoring is conducted to ensure that the rights and well-being of trial participants are protected, that the reported trial data are accurate, complete, and verifiable, and that the conduct of the trial is in compliance with the currently approved protocol, with International Conference on Harmonisation Good Clinical Practice (ICH GCP), and with applicable regulatory requirement(s).

Authorized, qualified clinical research associate (CRA) of Integra LifeSciences will accomplish the monitoring of the collected retrospective data per the study specific clinical monitoring plan.

The investigator and study staff will allocate adequate time for such monitoring activities. The investigator will also ensure that the monitor or other compliance or quality assurance reviewer is given access to all the study-related documents. The site will participate in an initiation visit and will be trained on the study protocol, the eCRF and study related responsibilities. One on-site visit will occur once the study site has completed the eCRFs, so that the Clinical research Associate from Integra LifeSciences can verify the collected data to the source documents (100% source data verification).

The onsite Close-Out Visit may be a combined visit with the monitoring visit.

# 7 Safety Assessments and Reporting

#### 7.1 Definitions

The table below contains the definitions being used for safety assessment as part of this study:

**Table 2: List of AE Terms and Definitions** 

This list of terms should be edited to remove those which do not concern the study.						
Term	Definition					
Adverse Device	An adverse event related to the use of an investigational medical					
Effect (ADE)	device. This definition includes adverse events resulting from					
	insufficient or inadequate instructions for use, deployment,					
	implantation, installation, or operation, or any malfunction of the					
	investigational medical device. And this definition includes any event					
	resulting from use error or from intentional misuse of the					
	investigational device.					
Adverse Event (AE)	Any untoward medical occurrence, unintended disease or injury, or					
	untoward clinical signs (including abnormal laboratory findings) in					
	subjects, users, or other persons, whether or not related to the					
	investigational medical device and whether anticipated of					
	unanticipated.					
	This definition includes events related to the investigational medical					
	device; events related to the procedures involved and, for users or					
	other persons, this definition is restricted to events related to					
	investigational medical devices.					
Anticipated Serious	A serious adverse device effect which by its nature, incidence,					
Adverse Device Effect (ASADE)	severity or outcome has been identified in the risk assessment					
Device Deficiency	Inadequacy of a medical device with respect to its identity, quality,					
(DD)	durability, reliability, usability, safety or performance.					
	Note 1: Device deficiencies include malfunctions, use errors, and					
	inadequacy in the information supplied by the manufacturer including labelling.					
	Note 2: This definition includes device deficiencies related to the					
	investigational medical device or the comparator.					

This list of terms should be edited to remove those which do not concern the study.				
Term	Definition			
Malfunction	Failure of an investigational medical device to perform in accordance			
	with its intended purpose when used in accordance with the			
	instruction for use.			
Serious Adverse	Adverse device effect that has resulted in any of the consequences			
Device Effect (SADE)	characteristic of a serious adverse event.			
	Note: SAEs related to procedures imposed by the clinical			
	investigation plan but not with the use of the device should not be			
	considered Serious Adverse Device Effects.			
Serious Adverse	Adverse event that led to any of the following:			
Event (SAE)	a) death,			
	b) serious deterioration in the health of the subject, users or other			
	persons as defined by one or more of the following:			
	a life-threatening illness or injury, or			
	a permanent impairment of a body structure or a body funct			
	including chronic diseases, or			
	in-patient or prolonged hospitalization, or			
	medical or surgical intervention to prevent life-threatening illness or			
	injury or permanent impairment to a body structure or a body function,			
	c) fetal distress, fetal death or a congenital abnormality or birth defect			
	including physical or mental impairment			
	Note: Planned hospitalization for a pre-existing condition, or a			
	procedure required by the CIP, without serious deterioration in health,			
	is not considered a serious adverse event.			
Unanticipated	Any serious adverse effect on health or safety or any life-threatening			
Adverse Device	problem or death caused by, or associated with, a device, if that effect,			
Effect (UADE)	problem, or death was not previously identified in nature, severity, or			
	degree of incidence in the investigational plan or application (including			
	a supplementary plan or application), or any other unanticipated			
	serious problem associated with a device that relates to the rights,			
	safety, or welfare of subjects			

This list of terms should be edited to remove those which do not concern the study.			
Term	Definition		
Unanticipated	Serious adverse device effect which by its nature, incidence, severity		
Serious Adverse Device Effect	or outcome has not been identified in the current risk assessment.		
(USADE)	Note 1: Anticipated serious adverse device effect (ASADE) is an		
(00.122)	effect which by its nature, incidence, severity or outcome has been		
	identified in the risk assessment.		
	Note 2: Procedures associated with the use of a device should be		
	addressed in the risk assessment, which makes it possible to		
	determine whether the procedure related SAEs are Unanticipated		
	Serious Adverse Device Effect or not.		

## 7.2 Reporting of Safety Information

## 7.2.1 Non-Reportable Event

All Adverse Events, related or not related to the study device or study index procedure by the investigator, are required to be reported in this study.

# 7.2.2 Severity

Each adverse event will be classified according to three (3) levels of severity. The Sponsor and the investigator will use the following definitions to assess the severity of the adverse event:

**Mild** – Awareness of signs or symptoms, but easily tolerated and are of minor irritant type causing no loss of time from normal activities. Symptoms do not require therapy or a medical evaluation; signs and symptoms are transient.

**Moderate** – Events introduce a low level of inconvenience or concern to the participant and may interfere with daily activities, but are usually improved by simple therapeutic measures; moderate experiences may cause some interference with functioning

**Severe** – Events interrupt the participant's normal daily activities and generally require systemic drug therapy or other treatment; they are usually incapacitating

#### 7.2.3 Causality

The relationship between the use of the medical device (including the medical - surgical procedure) and the occurrence of each adverse event shall be assessed and categorized.

Each AE will be classified according to four (4) different levels of causality:

**Not related**: Relationship to the device, or procedures can be excluded when:

- the event has no temporal relationship with the use of the study devices, or the procedures related to application of the study devices;
- the serious adverse event does not follow a known response pattern to the medical device (if the response pattern is previously known) and is biologically implausible;
- the discontinuation of medical device application or the reduction of the level of activation/exposure when clinically feasible and reintroduction of its use (or increase of the level of activation/exposure), do not impact on the serious adverse event;
- the event involves a body-site or an organ that cannot be affected by the device or procedure;
- the serious adverse event can be attributed to another cause (e.g., an underlying or concurrent illness/ clinical condition, an effect of another device, drug, treatment or other risk factors);
- the event does not depend on a false result given by the investigational device used for diagnosis, when applicable;

In order to establish the non-relatedness, not all the criteria listed above might be met at the same time, depending on the type of device/procedures and the serious adverse event

**Possible:** The relationship with the use of the investigational device or comparator, or the relationship with procedures, is weak but cannot be ruled out completely. Alternative causes are also possible (e.g., an underlying or concurrent illness/ clinical condition or/and an effect of another device, drug or treatment). Cases where relatedness cannot be assessed, or no information has been obtained should also be classified as possible.

**Probable:** The relationship with the use of the investigational device or comparator, or the relationship with procedures, seems relevant and/or the event cannot be reasonably explained by another cause.

**Causal relationship:** the serious adverse event is associated with the investigational device, or with procedures beyond reasonable doubt when:

- the event is a known side effect of the product category the device belongs to or of similar devices and procedures;
- the event has a temporal relationship with investigational device use/application or procedures;
- the event involves a body-site or organ that
  - o the investigational device or procedures are applied to;

- o the investigational device or procedures have an effect on;
- the serious adverse event follows a known response pattern to the medical device (if the response pattern is previously known);
- the discontinuation of medical device application (or reduction of the level of activation/exposure) and reintroduction of its use (or increase of the level of activation/exposure), impact on the serious adverse event (when clinically feasible);
- other possible causes (e.g., an underlying or concurrent illness/ clinical condition or/and an effect of another device, drug or treatment) have been adequately ruled out;
- harm to the subject is due to error in use;
- the event depends on a false result given by the investigational device used for diagnosis, when applicable;

In order to establish the relatedness, not all the criteria listed above might be met at the same time, depending on the type of device/procedures and the serious adverse event.

The Sponsor and the investigator will distinguish between the adverse events related to the study device and those related to the procedures (any procedure specific to the study). An adverse event can be related both to procedure and the study device.

During causality assessment activity, clinical judgement shall be used and the relevant documents, such as the IFU, the Clinical Investigation Plan or the Risk Analysis Report shall be consulted, as all the foreseeable serious adverse events and the potential risks are listed and assessed there. The presence of confounding factors, such as concomitant medication/treatment, the natural history of the underlying disease, other concurrent illness or risk factors shall also be considered.

Complications caused by concomitant treatments not imposed by the clinical investigation plan are considered not related. Similarly, several routine diagnostic or patient management procedures are applied to patients regardless of the clinical investigation plan. If routine procedures are not imposed by the clinical investigation plan, complications caused by them are also considered not related.

In some particular cases the event may not be adequately assessed because information is insufficient or contradictory and/or the data cannot be verified or supplemented. The Sponsor and the investigator will make the maximum effort to define and categorize the event and avoid these situations. Where an investigator assessment is not available and/or the Sponsor remains uncertain about classifying the adverse event, the sponsor should not exclude the relatedness; the event should be classified as "possible" and the reporting not be delayed.

Particular attention shall be given to the causality evaluation of unanticipated serious adverse events. The occurrence of unanticipated events related to the use of the device could suggest that the clinical investigation places subjects at increased risk of harm than was to be expected beforehand.

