#### 2.2.1 Study Device Intended Purpose

The Gentrix Surgical Matrix Devices were used within label in this retrospective study. There were no specific medical or surgical procedures involved in the use of the study devices, other than the standard of care. A full description of the medical and surgical procedures related to the Gentrix Surgical Matrix Devices is available in the Instructions for Use.

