#### 9.3.5 Analysis of Adverse Events

The incidence rate of each of the adverse device effects through Index Surgery, Discharge and follow-up visit will be presented. The incidence of adverse events and serious adverse events will be tabulated (frequencies and percentage of patients) by severity and relationship to device and procedure. The analysis of safety will be performed in the enrolled population.

Descriptive statistics will be provided for safety endpoints by surgical procedure. All safety summaries will be presented for the full analysis population. Adverse Device Events will be coded according to Medical Dictionary for Regulatory Activities (MedDRA) AE coding dictionary. All ADEs will be listed. A summary of the frequency count and percentage of subjects reporting each ADE category will be produced for all reported ADEs and SADEs. Relationship of AE verbatim text to group terms and body systems will also be reported. A listing of withdrawals due to ADEs will be provided. Deaths and SADEs will be listed should they occur.

AE listing includes Onset Date, AE Term, Relation to Device, Relation to Procedure, Pattern, Seriousness (SAE), Severity, Treatment, Medication, Surgical, Outcome, End Date. By subject listings will be provided for each subject reported.

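### Protocol 7.2.3 contradicts itself on whether the index hernia repair counts as a procedure for adverse-event causality, so operative complications can be coded as not related

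*Protocol*

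**What the plan says.** **The narrow text.** Near the end of Protocol 7.2.3, the sponsor and investigator are told to separate device-related events from "those related to the procedures (any procedure specific to the study". Two exclusion sentences follow. The first treats complications of concomitant treatments that the plan did not impose as unrelated. The second observes that "several routine diagnostic or patient management procedures are applied to patients regardless of the clinical investigation plan" and concludes: "If routine procedures are not imposed by the clinical investigation plan, complications caused by them are also considered not related".

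**The status of the repair.** Under Study Device Intended Purpose the protocol states: "There were no specific medical or surgical procedures involved in the use of the study devices, other than the standard of care". Section 5.7.2 adds: "Participation in the study does not submit the patient to any additional procedures or exams outside the customary standard of care". The synopsis and section 5.6 describe the device as having been used in routine, standard-of-care practice.

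**The wide text.** Section 7.2.3 opens by placing under assessment "The relationship between the use of the medical device (including the medical - surgical procedure". Its criteria for an unrelated event mention "the procedures related to application of the study devices". Section 7.2.1 names the index procedure, alongside the device, as something an event may be related to.

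**Where the judgement is used.** Protocol 7.3.1 has the relationship to product and to study procedure recorded for each event. SAP 9.3.5 tabulates adverse events and serious adverse events "by severity and relationship to device and procedure". Protocol 10.4.6 counts subjects with any related event. None of these three defines procedure, and 10.4.6 does not define related.

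**The concern.** The narrow text suits a prospective investigation, where the plan adds procedures and their harms must be told apart from those of background care. Here the surgery was over before the plan existed. If only procedures specific to the study count, and the study has none, then a dehiscence or bowel injury that the investigator puts down to the operation alone has nowhere to go but the not-related category.

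The study aims to confirm safety and to find unknown side-effects. A reader of the report will use the relationship tables to tell harm of the graft from harm of the operation. If the procedure column rests on an unsettled definition, that reading is unsafe, and any error from the narrow rule runs one way, toward fewer related events.

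**Working it through.** The plan states no figure on this point, so the check is a comparison of texts, followed by one small calculation on what a zero would mean.

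1. **What counts as a procedure under the narrow text?** Only one specific to the study.
2. **Does the study contain any?** Study Device Intended Purpose reports nothing beyond standard of care, and 5.7.2 says that participation adds no procedure or exam. Read literally, the set is empty.
3. **Do the exclusion sentences reach the repair?** The second refers back to routine diagnostic or patient-management procedures, which need not include implant surgery. But the synopsis and 5.6 call the treatment routine, and no sentence exempts the repair. The point is open.
4. **Does other text include the repair?** Yes: the opening of 7.2.3, its reference to procedures that apply the device, and the index procedure named in 7.2.1.
5. **Which text governs?** Nothing says. The instruction in 7.2.3 to default to possible applies when an assessment is missing, insufficient or uncertain. It does not help when a rule directs not related.
6. **What happens to one event?** Take a dehiscence that the investigator attributes to the operation and not to the graft. Under the narrow text it is not related to procedure. Under the wide text it is possible, probable or causal. Either coding complies with 7.2.3.
7. **Where does the difference show?** In the procedure-relationship columns of SAP 9.3.5. It also shows in the any-related count of Protocol 10.4.6, but only if that count includes procedure-related events.

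**What a zero would mean.** The planned size is about 35 (Protocol 10.2, SAP 8). Under the literal narrow reading the procedure-related count is 0/35 = 0% whatever happened. The exact 95% upper limit would be 1 − 0.025^(1/35) = 10.0%, which would look like evidence of a low rate. If the true share of subjects with a procedure-related event is p, the chance of at least one among 35 is 1 − (1 − p)^35. The documents give no p, so these values are assumptions:

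- p = 5%: 1 − 0.95^35 = 83.4%
- p = 10%: 1 − 0.90^35 = 97.5%
- p = 20%: 1 − 0.80^35 = 99.96%

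Over that range an empty column would more likely reflect the coding rule than the charts. This does not estimate how much undercounting will occur.

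**The case against.** The strongest reply is that a coder who reads all of 7.2.3 would not exclude the repair. The exclusion sentence points back to background diagnostic and management care, and is paired with concomitant treatments. The index operation is how the device is implanted, so it fits neither class naturally. The causal criteria refer to known side effects of similar devices and procedures and to body sites where procedures are applied. The section sends the assessor to the Instructions for Use, whose listed events in 7.2.4 include seroma, fistula, hematoma and bowel injury. This stands in part: the text permits the miscoding but does not compel it. It does not cure the restriction to procedures specific to the study, which a standard-of-care operation fails on its face.

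A reader might also infer three stronger things that the documents do not support.

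- **That the device will look safer.** Relationship to device is judged separately, and emptying the procedure column does not directly change it.
- **That the overall related-event rate falls by a definable amount.** Protocol 10.4.6 does not say whether related includes procedure-only events, and its tie-break for repeated events refers to the device. If related means device-related, events due to surgery alone are outside the count under either reading.
- **That the safety objective is defeated.** That objective is to capture complications, with no causality filter. All adverse events are to be listed by subject, and subjects with any event are counted.

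**Conclusion.** The contradiction is real and sits inside one section. Followed literally, the closing part of 7.2.3 lets complications of the hernia repair be coded as unrelated to procedure, while 7.2.1 and the earlier part of 7.2.3 treat the operation as in scope. The consequence is understated or inconsistent coding in the procedure-relationship columns for adverse events and serious adverse events, and in the any-related count if it covers procedure-related events.

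No size can be derived from the documents. It depends on how many events the investigator attributes to surgery alone and on which text is followed, and neither is given. The primary endpoint and the surgical site occurrence and infection endpoints, as defined, carry no causality condition and are unaffected. The study is descriptive and tests no hypothesis, so no decision rule turns on these columns. What is at stake is whether the safety tables can be interpreted, which is reason enough to settle the wording before events are coded.

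**What to change.** - In Protocol 7.2.3, replace the parenthesis that limits procedures to those specific to the study with the index hernia repair, including graft placement, fixation and any component separation.
- Limit the two sentences about treatments and procedures that the plan did not impose to care unconnected with the index repair.
- Use the same definition of procedure in Protocol 10.4.6 and SAP 9.3.5, and state in 10.4.6 whether a related event means related to device, to procedure, or to either.

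The cost is wording in the protocol, the SAP and any case report form guidance. It needs no new data and no change in sample size. It should come before coding, because relatedness is a judgement made event by event; any events already coded would need another look. The sponsor should accept that the related-event percentage may become less favourable.
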